5.1. Pulsed Inhaled Nitric Oxide for Treatment of Long-Term Pulmonary Arterial Hypertension

The effects of long-term administration of iNO to patients with PAH, chronic obstructive pulmonary disease (COPD), and idiopathic pulmonary fibrosis (IPF) have been published. Approximately 100 patients received iNO acutely, approximately 40 of whom continued to receive long-term iNO for up to 2 years (Ashutosh 2000, Channick 1996, Germann 1998, Perez-Penate 2005, Perez-Penate 2008, Vonbank 2003, Yung 2001). Overall, review of the published medical literature and clinical experience indicates that iNO at doses of 0.013 to 0.1 mg/kg per hour for up to 2 years appears safe and suggests efficacy for the treatment of pulmonary hypertension (PH), including Pulmonary Hypertension Group 1.

Inhaled NO offers an additional treatment option for patients, in particular patients who are already receiving prostacyclin therapy, ERA, and PDE-5, who have no other medical treatment options. Inhaled NO has the advantage of being able to be added to all other available PAH therapies with the exception of riociguat. The riociguat label excludes addition of NO donors because of the side effects of systemic hypotension.

Bellerophon Pulse Technologies recently completed Part 1 of a Phase 2 clinical trial of iNO/INOpulse for PAH in the United States and Canada (Study IK-7001-PAH-201). The key inclusion criteria for subjects in this trial were: pulmonary hypertension WHO Group I, on at least one other PAH medication for at least 12 weeks prior to treatment with iNO/INOpulse, and demonstrated ability to walk between 100 and 450 meters within 6 minutes. The Part 1 placebo-controlled, double-blind clinical trial randomized 80 subjects in a 1:1:1 fashion to placebo or to one of two active iNO doses—25 or 75 mcg/kg IBW/hr for 16 weeks. Subjects who completed Part 1 of the trial were able to enroll in an open-label, long-term extension portion of the study (Part 2), in which all subjects received one of two doses iNO. The objective in Part 2 was to explore the long-term safety and tolerability of therapy.

The primary endpoint of Part 1 was change in pulmonary vascular resistance (PVR) from baseline at 16 weeks, and the main secondary endpoint was change in placebo-adjusted 6-minute walk distance (6MWD) over the same period. The baseline characteristics seemed to indicate that subjects in the iNO groups had more severe disease. LTOT use at baseline was 78% and 59% in the 75 and 25 mcg/kg IBW/hr cohorts, respectively, compared to 46% in the placebo cohort. Baseline PVR values were higher in the higher dose group, and 6MWDs were lower in the same group. The results in the ITT population showed a trend toward a lowering of PVR with iNO treatment and an increase in 6MWD, but this did not reach statistical significance.

Adherence to therapy was widely variable. LTOT use was recorded at baseline, and subjects using LTOT at baseline were more adherent to using the investigational INOpulse delivery device (hereafter INOpulse device), defined retrospectively as an average use of ≥ 12 hours per day—specifically, subjects using LTOT had a rate of 71% adherence as compared with 32% adherence in those subjects not using LTOT. Based on this finding, we conducted post hoc, exploratory analyses of LTOT combined with iNO for ≥ 12 hours a day.

In the post-hoc, unplanned analyses, the subgroup of subjects who used the INOpulse device for an average ≥ 12 hours per day with LTOT ($n = 35$), showed a positive trend towards a decrease in PVR with 25 and 75 mcg/kg IBW/hr. There was a clinically meaningful improvement in 6MWD in comparing the 75 mcg/kg IBW/hr dose group with the placebo group (52 ± 42 [mean \pm SD] vs. -17 ± 32 [mean \pm SD]). There was on average a non-significant increase in 6MWD of 26 meters in subjects treated with 25 mcg/kg IBW/hr. Improvements in 6MWD were the same for subjects treated with oral PAH therapies alone, and subjects with prostacyclin therapy plus therapy with either a PDE-5 or ERA. The results were similar to those subjects with inhaled iloprost where there was no significant change in PVR prior to inhalation of iloprost at EOS versus baseline, but a significant improvement in 6MWD (Olschewski 2002).

Inhaled NO was relatively well-tolerated in Part 1 of the trial. The SAEs were balanced between all 3 cohorts (reference Investigator Brochure for additional detail).

Eighty-one percent of subjects elected to enter into the long-term extension trial.

The results of Part 2 of the study demonstrated that pulsed iNO was well tolerated beyond the initial 16-week treatment period in Part 1. The incidence of Respiratory AEs and related Respiratory AEs in the Part 2 of the study were comparable in both the iNO 75 and iNO 25 treatment groups. No subjects had a MetHb level $\geq 7\%$.

Subjects with LTOT are more likely to be compliant and may have better outcomes. In the Phase 3 trial, recruitment will be limited to only subjects on LTOT.

5.2. Inhaled Nitric Oxide

Inhaled nitric oxide, a prescription pharmaceutical drug under the brand name of INOmax[®] (nitric oxide) for inhalation, is available commercially as a gaseous mixture of NO and nitrogen (N₂). INOmax is approved and marketed by Ikaria Inc. (now owned by Mallinckrodt Pharmaceuticals) and The Linde Group in the US (December 1999), European Union (August 2001) and other national authorities, for neonates (> 34 weeks old) with hypoxic respiratory failure associated with clinical or echocardiographic evidence of PH when used in conjunction with ventilatory support and other appropriate agents.

Nitric oxide is a selective pulmonary vasodilator. The mechanism of NO-mediated vasodilation occurs via the activation of soluble guanylate cyclase, the production of cyclic guanosine monophosphate (cGMP), and subsequent relaxation of vascular smooth muscle. Inhaled NO produces pulmonary vasodilation and clearly does not affect systemic vascular beds by virtue of its high affinity for hemoglobin and rapid inactivation. In a number of animal species and under several vasoconstrictive stimuli, iNO produced rapid and effective pulmonary vasodilation at concentrations between 5 and 80 parts per million (ppm). Evaluations in the newborn lamb demonstrated that iNO selectively reverses hypoxic pulmonary vasoconstriction, with maximal pulmonary vasodilation produced by NO concentrations of 80 ppm. In an animal model of persistent PH of the newborn (PPHN), neonatal lambs displayed a marked and rapid pulmonary vasodilation that improved oxygenation at inhaled NO concentrations of 100 ppm.

5.3. INOpulse Device

For the indication of PAH, iNO is being developed as a drug/device combination therapy to be used with the INOpulse delivery device.

The INOpulse device is a complete, integrated system that uses a 0.074 liter aluminum cartridge containing a concentration of 6.0 mg/L (4880 ppm) of NO gas. The device is lightweight, portable, allowing NO to be administered via a nasal cannula to spontaneously breathing subjects. These features make it ideal for use in an ambulatory setting. The main advantage of the INOpulse device for spontaneously breathing subjects lies in its ability to deliver precise, preset NO doses over time, independent of the subject's respiration rate and tidal volume. Prescribed doses of iNO are delivered through the INOpulse according to amount of drug per ideal body weight (IBW) per hour (i.e., mcg/kg IBW/hr). The iNO dose is pulsed over the first half of the subject's inspiration rather than inhaled throughout the entire inspiratory period and the hourly set dose is accurately delivered throughout the hour.

6. OBJECTIVES

Part 1 Blinded Treatment Period

6.1. Primary Objective

The primary objective in this study is to evaluate the efficacy of iNO on exercise using 6-minute walk distance (6MWD) in subjects with PAH currently receiving background PAH medication and LTOT.

6.1.1. Secondary Objectives

The secondary objectives in this study are:

1. To evaluate the time to clinical worsening (TTCW)
2. To evaluate change in World Health Organization (WHO) Functional Class

6.1.2. Safety Objectives

The safety objectives in this study are to evaluate the safety and tolerability of iNO.

6.1.3. Tertiary Objectives

The tertiary objectives in this study are:

1. To evaluate changes in health-related quality of life using the Short Form-36 (SF-36) version 2 health survey
2. To evaluate the impact of iNO on pulmonary hemodynamics in a subset of subjects
3. To evaluate the changes in right ventricular (RV) and left ventricular (LV) function as measured by echocardiography, in a subset of subjects
4. To evaluate change in N-terminal of the prohormone brain natriuretic peptide (NT-proBNP)
5. To evaluate change in Borg dyspnea score immediately following 6-minute walk test (6MWT)
6. To evaluate change in 6MWD as related to degree of correlation between drug adherence and clinical efficacy measurement
7. To evaluate subjects with unsatisfactory clinical response
8. To evaluate the impact of iNO on frequency of heart-lung or lung transplantation, and deaths while awaiting transplantation
9. To evaluate the impact of iNO on medical resource utilization

6.2. Part 2 -Open Label Period:

6.2.1. Primary Objective:

1. To Evaluate the long term safety and tolerability of iNO

6.2.2. Secondary Objective:

1. To evaluate the change in exercise tolerance in subjects who switch from placebo to active therapy

7. ENDPOINTS

7.1. Part 1 Blinded Treatment Period

7.1.1. Primary Endpoint

The primary endpoint in this study is to assess the efficacy of iNO as measured by the placebo-adjusted change in 6MWD from baseline to 18 weeks.

7.1.2. Secondary Endpoints

The secondary endpoints include:

1. TTCW, the time (in days) from start of treatment to first event (first day the event is noted), with iNO as compared to placebo, measured from baseline to 18 weeks. TTCW event is defined as any of the following:
 - a. Death (all-cause mortality)
 - b. Atrial septostomy
 - c. Hospitalization due to worsening of PAH (adjudicated)
 - d. Start of new specific PAH treatment (endothelin receptor antagonists [ERAs], phosphodiesterase type-5 [PDE-5] inhibitors or prostanoids), an increase in the dose of an ERA or PDE-5, increase in the dose or frequency of an inhaled prostanoids, or an increase in the dose of an intravenous or subcutaneous prostanoids by >10%.
 - e. Decrease of >15% from baseline or >30% compared with the last study related measurement in 6MWD should be confirmed by a repeat measurement performed at least 14 days later
 - f. Worsening of WHO Functional Class (e.g., from Class II to Class III or IV, OR Class III to Class IV); and should be confirmed by a repeat assessment at least 14 days later
2. Change in WHO Functional Class, with iNO as compared to placebo, from baseline to 18 weeks

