There is no cure for PAH and the 5-year survival rate for idiopathic or heritable PAH was approximately 30% prior to the availability of targeted PAH therapies based on Registry data from the 1980s (Anderson 2010). However, in recent years, effective therapies targeting specific endothelial abnormalities have emerged. Currently approved treatments have been demonstrated to have both short- and long-term efficacy. These include: synthetic prostacyclin, i.e., epoprostenol, a prostacyclin analog, treprostinil or iloprost; an endothelin receptor antagonist (ERA), i.e., bosentan, ambrisentan, or macitentan; phosphodiesterase type-5 (PDE-5) inhibitors, i.e., sildenafil and tadalafil; and soluble guanylate cyclase (sGC) stimulators, i.e., riociguat (McLaughlin 2006; Barst 2009; McGoon 2009; Badesch 2007; Anderson 2010; Ghofrani 2013). These medications may improve symptoms, exercise capacity, and clinical outcome, but may be limited by either parenteral delivery system, the need for frequent laboratory monitoring, frequent dosing schedules, or unwanted side effects. Because of the availability of several agents working via different mechanisms, interest has developed in add on (i.e., combination) therapy. This strategy has proven successful in improving clinical outcomes in some subjects. Yet, as stated above, despite these significant advances in the treatment of PAH, the current 5-year survival for Group 1 PAH is ~60% utilizing the available approved PAH therapies (Anderson 2010). Patients who are receiving prostacyclin therapy, ERA, and PDE-5, have no further treatment options other than atrial septostomy and lung transplantation.

PAH is associated with impaired release of nitric oxide at least in part because of reduced expression of nitric oxide synthase in the vascular endothelium of pulmonary arteries (McLaughlin 2009; Barst 2009; McGoon 2009; Badesch 2007; Anderson 2010). Thus, chronic administration of iNO may be viewed as replacement therapy in some subjects with PAH making it a logical choice for clinical evaluation.

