10.1. Subject Discontinuation from Study Drug/Device

Any subject who is discontinued from the study drug will be encouraged to perform all procedures and assessments as appropriate until week 18. Vital status will be determined at the EOS on all subjects who prematurely discontinue. The specific reason for discontinuation will be documented in the eCRF. Subjects may be discontinued due to the following:

1. In the opinion of the Investigator, it is in the subject's best interests to discontinue study drug.
2. Subject no longer wishes to continue using the drug/device.
3. A subject becomes pregnant.
4. In the opinion of the Investigator, the subject experiences clinically significant rebound PH temporally associated with acute withdrawal of study drug.
5. If a subject experiences any of the following: death, atrial septostomy, lung or heart-lung transplantation.

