11.1.3.2. PAH Specific Therapies

Specific attention will be paid to PAH specific and supporting therapies. Each dose of any specific PAH therapy should be recorded, including ERA, PDE-5 inhibitor, prostacyclin or a prostacyclin analog. If addition of riociguat is required, the subject will need to be discontinued from study drug, but should remain in study and complete all assessments until EOS. Increases in prostanoid dose may be necessary over the length of the study due to tachyphylaxis and will not be considered a TTCW event. The addition of prostanoid therapy or increases in prostanoid dose as a TTCW event will be determined by the ICEC.

LTOT flow rates should be kept constant throughout the study unless the subject has persistent desaturations to less than 88% of SpO₂, or otherwise clinically indicated. LTOT flow rate with the estimated length of use per day must be documented in the eCRF at all visits.

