14.1. Allowed PAH Approved Medication Changes During the Study

Currently approved treatments include: synthetic prostacyclin (i.e., epoprostenol, a prostacyclin analog, treprostinil or iloprost), an ERA (i.e., bosentan, ambrisentan, or macitentan), and PDE-5 inhibitors (i.e., sildenafil and tadalafil).

PAH therapies may be altered or additional therapies added only for evidence of clinical worsening due to PAH as defined in the protocol throughout the trial.

LTOT flow rates should be kept constant throughout the study unless the subject has persistent desaturations to less than 88% of SpO₂, or otherwise clinically indicated. LTOT flow rate with the estimated length of use per day must be documented in the eCRF at all visits.

All PAH approved medications should be given as per standard of care, with the exception that inhaled prostaglandins (Ventavis[®] and Tyvaso[®]) and oral sildenafil doses should be not be given within 1 hour of a scheduled RHC.

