16.3.2. Secondary Efficacy Endpoints

The secondary efficacy endpoints include:

1. TTCW*: The time (in days) from start of treatment to first event (first day the event is noted), with iNO as compared to placebo, measured from baseline to week 18. TTCW event is defined as any of the following:
 - a. Death (all-cause mortality)
 - b. Atrial septostomy
 - c. Hospitalization due to worsening of PAH (adjudicated)
 - d. Start of new specific PAH treatment (endothelin receptor antagonists [ERAs], phosphodiesterase type-5 [PDE-5] inhibitors or prostanoids), an increase in the dose of an ERA or PDE-5, increase in the dose or frequency of an inhaled prostanoids, or an increase in the dose of an intravenous or subcutaneous prostanoids by >10%.
 - e. Decrease of >15% from baseline or > 30% compared with the last study related measurement in 6MWD and should be confirmed by a repeat measurement performed at least 14 days later
 - f. Worsening of WHO Functional Class (e.g., from Class II to Class III or IV, OR Class III to Class IV); and should be confirmed by a repeat assessment at least 14 days later
2. Change in WHO Functional Class, with iNO as compared to placebo, from baseline to 18 weeks.

The TTCW endpoint will be analyzed with log-rank test stratified by the prostanoid usage status. The censoring time points for the analyses include the time points at which subjects drop out of the study or complete the study without any of the specified events.

The WHO Functional Class endpoint will be analyzed with the same method as that for the primary endpoint. Change from baseline to week 18 will also be evaluated as an exploratory analysis.

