### 7.4.1 Time (in days) to First Clinical Worsening Event (TTCW)

Time to First Clinical worsening event from baseline to week 18 will be analyzed with log-rank test stratified by the prostanoid usage status (Table 26) for blinded period of study. All Individual criteria's to be analyzed using the same model as TTCW.

The censoring time points for the analyses include the time points at which subjects drop out of the study or complete the study blinded treatment period (week 18) without any of the specified events.

Time (in days) to first clinical worsening (TTCW) will be defined as time from randomization to either of the below mentioned events:

- i. Death (all-cause mortality)
- ii. Atrial septostomy

- iii. Hospitalization due to worsening of PAH (adjudicated)
- iv. Start of new specific PAH treatment (endothelin receptor antagonists [ERAs], phosphodiesterase type-5 [PDE-5] inhibitors or prostanoids), an increase in the dose of an ERA or PDE-5, increase in the dose or frequency of an inhaled prostanoids, or an increase in the dose of an intravenous or subcutaneous prostanoids by >10%.
- v. Decrease of >15% from baseline or >30% compared with the last study related measurement in 6MWD should be confirmed by a repeat measurement performed at least 14 days later
- vi. Worsening of WHO Functional Class (e.g., from Class II to Class III or IV, OR Class III to Class IV); and should be confirmed by a repeat assessment at least 14 days later

Patients who did not experience clinical worsening at the time of statistical analysis will be censored at the time of subject's last visit in part I phase, this includes patients who are lost to follow-up or have withdrawn consent.

Time to first clinical worsening (TTCW) Calculation:

1. Always calculated from date of randomization
2. If a patient discontinues study treatment prior to any of the above mentioned events then patient's last visit will be considered for censoring.
3. Patients who have not experienced TTCW will be censored at the last evaluable assessment. This includes patients who are lost to follow up or have withdrawn consent.
4. If a patient has no evaluable baseline assessment then TTCW will be censored at 0 days.
5. If a patient has no evaluable post baseline assessment then TTCW will be censored at 0 days.
6. Censoring variables for each of the individual criteria's will same as above.

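### The time-to-clinical-worsening definition counts rescue with three PAH drug classes and septostomy, but not a riociguat start or lung transplantation, so some worsening can be scored event-free

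*Protocol*

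**What the plan says.** TTCW is called a key secondary endpoint (Protocol 8.3) and is second in the gatekeeping order (Protocol 16.3.4). It has the same six components wherever it is set out in full: the synopsis, Protocol 7.1.2 and 16.3.2, SAP Table 3 and SAP 7.4.1. Component d begins "Start of new specific PAH treatment (endothelin receptor antagonists [ERAs], phosphodiesterase type-5 [PDE-5] inhibitors or prostanoids" and goes on to dose increases in those classes. Component b is atrial septostomy alone.

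Elsewhere the Protocol treats riociguat as a further class. The Introduction lists "soluble guanylate cyclase (sGC) stimulators, i.e., riociguat" among approved treatments, and section 11.1.3.2 says: "If addition of riociguat is required, the subject will need to be discontinued from study drug, but should remain in study". Section 9.4 excludes riociguat at entry and makes having started it the exclusion for Part 2.

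Section 10.1 opens its list of reasons for stopping study drug with "Subjects may be discontinued due to the following", and item 5 of that list reads "If a subject experiences any of the following: death, atrial septostomy, lung or heart-lung transplantation". Transplantation is otherwise counted only as tertiary endpoint 8.

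On censoring, Protocol 16.3.2 states "The censoring time points for the analyses include the time points at which subjects drop out of the study", or complete it without an event. SAP 7.4.1 adds, as rule 2 of its calculation list: "If a patient discontinues study treatment prior to any of the above mentioned events then patient's last visit will be considered for censoring".

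**The concern.** Two subjects with the same deterioration can be scored differently according to the drug class chosen for rescue: starting a PDE-5 inhibitor is an event, starting riociguat is not. The same split separates septostomy from transplantation.

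Two things are at stake. First, the composite can miss worsening it was built to detect. If the missed occurrences are commoner on placebo, benefit is understated; if commoner on iNO, harm is understated. Second, if such subjects are also censored when they stop study drug, the censoring follows from their deterioration, whereas the log-rank test assumes that censoring is unrelated to prognosis.

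**Working it through.** The documents give no TTCW event count, hazard ratio or power; the only sizing figures concern 6MWD. There is no stated figure to reproduce, so the check is mainly textual.

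**Step 1. Which occurrences count.**

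| Occurrence | Study drug | TTCW event? |
|---|---|---|
| Start of ERA, PDE-5 inhibitor or prostanoid | No stop required | Yes, component d |
| Start of riociguat | Must stop (11.1.3.2) | No |
| Death | Listed in 10.1, item 5 | Yes, component a |
| Atrial septostomy | May stop (10.1, item 5) | Yes, component b |
| Lung or heart-lung transplantation | May stop (10.1, item 5) | No; tertiary endpoint 8 only |

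Of the three occurrences in item 5, transplantation is the only one outside the composite. Of the four approved classes in the Introduction, the sGC stimulators are the only one outside component d.

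**Step 2. What happens to a subject with no other component.** Under Protocol 16.3.2 the subject stays at risk until leaving the study or finishing Week 18. SAP 7.4.1 has a general sentence that censors event-free subjects at their last visit in Part 1, then rule 2, which applies to those who stop study treatment and says only last visit. There are two readings:

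- *Last Part 1 visit.* The subject remains at risk and a later event can still count. The fault is an uncounted component; censoring at Week 18 is administrative.
- *Last visit on treatment.* The subject leaves the risk set at about the time of rescue. The component is uncounted and the censoring is also informative.

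The subject is scored event-free on both readings. Only the second adds informative censoring.

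**Step 3. How the SAP derives the event.** SAP Table 4 names no drug classes. It maps new PAH treatment one-to-one from a CRF module, and Table 26 is equally general. Programming might therefore pick up riociguat, contrary to the written definition. Table 4 has no transplant row.

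**Step 4. Size, under assumed inputs.** Schoenfeld approximation, 1:1 allocation, one-sided 0.025: power = Φ(√(D/4) × |ln HR| − 1.96), where D is the number of events. Suppose 10% of true events go uncounted and the hazard ratio is unchanged.

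- D = 25, HR 0.5: √6.25 × 0.693 − 1.96 = −0.227, power 41.0%. With D = 22.5: 37.6%.
- D = 40, HR 0.4: √10 × 0.916 − 1.96 = 0.938, power 82.6%. With D = 36: 78.5%.
- D = 15, HR 0.6: 16.6%, falling to 15.4%.

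For D of 15 to 40 and HR of 0.4 to 0.6 the loss is about 1 to 5 points. This covers lost events only. The bias from informative censoring cannot be computed from the documents.

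**The case against.** The strongest reply is that the gap is nearly empty. Protocol 14.1 says "PAH therapies may be altered or additional therapies added only for evidence of clinical worsening due to PAH as defined in the protocol", and section 8.1 says much the same. A compliant riociguat starter should therefore already have met a worsening criterion, and TTCW counts the first event.

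This holds for some subjects but does not close the gap. The same rule governs ERA, PDE-5 inhibitor and prostanoid starts, yet those count in their own right. Components e and f need confirmation at least 14 days later, by which time the subject may be on riociguat and off study drug. Section 14.1 also leaves riociguat out of its own list of approved treatments, so its reach is unclear, and it says nothing about transplantation.

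Other parts of the reply stand. A transplant admission may be adjudicated as a PAH hospitalization and count under component c. A transplant in a subject already listed at Screening need not reflect on-study worsening. Transplantation is prespecified as a tertiary endpoint with its own test, so leaving it out of TTCW can be defended as a choice, though no reason is given.

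A reader might infer that both occurrences force study-drug discontinuation and that all these subjects are censored at that moment. The documents do not support this. The stop is mandatory only for riociguat; section 10.1 is permissive for transplantation. Section 11.1.3.2 keeps riociguat starters under assessment to the end of study, and early censoring depends on one reading of the SAP's last visit.

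**Conclusion.** The point holds. Followed as written, the definition scores a riociguat start or a transplantation as no event unless another component is met, and the SAP leaves the censoring date of such a subject unclear. The censoring may be informative; the text does not establish that it is.

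The number of subjects affected over 18 weeks is unknown and may be small. A reader might set 2–5% of 188 subjects (3.8 to 9.4) against an assumed event rate of 15–20% (28 to 38 events) and infer that 10–33% of events are lost (3.8/38 to 9.4/28). That range should not be relied on: both rates are assumptions without a source in the documents, the limits pair opposite extremes, and it supposes that no affected subject has another qualifying event. The 1 to 5 point power loss is likewise only an illustration under assumed inputs.

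The primary 6MWD test does not depend on the TTCW definition. The correction is worth making because TTCW carries a confirmatory claim and the change is cheap.

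**What to change.** Before unblinding:

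1. In the synopsis, Protocol 7.1.2 and 16.3.2, SAP Table 3 and SAP 7.4.1, add soluble guanylate cyclase stimulators (riociguat) to component d, and lung or heart-lung transplantation to component b.
2. In SAP Table 4, state that the new-treatment mapping includes riociguat, and add a transplant row. SAP Table 15 names a Total Lung Capacity module as the source of transplant status, so confirm the source first.
3. Date the event at the first riociguat dose or at surgery.
4. In SAP 7.4.1, state that subjects who stop study drug but remain in the study stay at risk until their last Part 1 assessment.
5. Report the composite as now written as a sensitivity analysis.

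The cost is Protocol and SAP wording. PAH therapies (Protocol 11.1.3.2) and transplant status at each visit (11.1.25) are already recorded, so the change can be applied retrospectively to blinded data; check that the date of surgery is captured. The downside is a composite slightly different from the one in force for subjects already enrolled, which item 5 addresses. This changes endpoint scoring only, not any treatment rule.
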